5.1.2. Time When metHb Level Reached 50% Reduction

To estimate the time when a 50% reduction would be obtained, the following linear interpolation will be applied.

$T_{50} \text{ (minutes after first dose)} = (\text{baseline}/2) / [60 * (\text{baseline} - \text{metHb}_1) / \text{time of metHb}_1 \text{ in minutes}]$

T50 for the above example is 44 minutes.

$$T_{50} = (74/2) / \{ [(74.4 - 15.7) / 70] / 74.4 \} = 37.2 / 0.838571428 = 44.36$$

The units for T50 will be converted to hours by $T_{50} / 60$ in the dataset.

Due to the mathematical property of this derivation, a patient could never achieve 50% reduction at 1-hour post dosing if the first postdosing metHb was taken after 2 hours. Hence, this derivation will be applied only to those patients who had first postdosing metHb before 2 hours.

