3.2. Analysis Population

The following analysis sets will be identified for data summary.

Enrolled Analysis Set: All patients who sign the informed consent or otherwise meet all local enrollment criteria for the study are considered to have enrolled.

Safety Analysis Set: The safety set will include all enrolled patients who are treated with at least 1 ProvayBlue™ infusion dose. The safety analysis set will be used for safety data summary. Specifically, the safety population will include all treated patients from the Interventional Study and the Observational Study.

Efficacy Analysis Set: The efficacy analysis set includes all safety analysis set patients who have at least 1 metHb assessment before and after ProvayBlue™ infusion and who are Primary cases. This analysis set will be used for efficacy endpoint evaluation.

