3.7.2. Patient Groups by Methemoglobinemia Suspected Causative Agent

Patients are grouped in 2 subsets based on their methemoglobinemia suspected causative agent: Group 1 includes all patients that metHb was associated with Dapsone use, and Group 2 includes all non-Dapsone-caused metHb. The differentiation is primarily based on

- the frequency with which Dapsone is expected to be identified as the causative agent for inducing methemoglobinemia, and
- the long half-life of Dapsone and its metabolite dapsone hydroxylamine, which likely results in ongoing production of metHb through the acute treatment phase, in contrast to short-acting inciting agents such as amyl nitrate, where normal physiologic conversion of metHb to hemoglobin may begin shortly after exposure.

Patient group will be used for data summary tables.

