5.1.1. MetHb Level at 1-hour Post Dosing

The timing of postdosing metHb level assays is inconsistent in clinical practice and may not be obtained until hours after the conclusion of first dose infusion in the emergency department. It should be noted that, consistent with such practice, the Observational Study does not have a prespecified schedule for metHb postdosing collection. MetHb level at 1-hour postdosing will be derived using linear interpolation. This method will be referred to as backward linear interpolation if the first postdosing metHb was after 1 hour, or forward linear interpolation if the first postdosing metHb was before 1 hour. This method will be mathematically expressed as follows.

Step 1: calculate rate of metHb change per minutes)

$$= (\text{metHb_1} - \text{baseline}) / \text{time of metHb_1 in minutes}$$

Step 2:

$$\text{metHb_1hr} = \text{baseline} + 60 * [(\text{metHb_1} - \text{baseline}) / (\text{time of metHb_1 in minutes})]$$

where

- baseline = baseline metHb defined as the last metHb before the first dose of study drug)
- metHb_1 = first post treatment metHb observation
- constant (60) converted the time units from minutes to hours

For example, a patient has metHb of 74.40 at baseline and 15.70 at 70 minutes postdosing. The estimated metHb_1hr is 24.08571.

Percent change from baseline (PCHG) at 1-hour post dosing can be estimated as follows.

$$\text{PCHG (\%)} \text{ at 1-hour post dosing} = 100 * [(\text{metHb_1} - \text{baseline}) / \text{time of metHb_1 in minutes}] / \text{baseline}$$

The PCHG for the above example is -67.63%.

$$\text{PCHG at 1-hour} = 100 * \{ [60 * (15.7 - 74.4) / 70] / 74.4 \}$$

Due to the mathematical property of this derivation, a patient could never achieve 50% reduction at 1-hour post dosing if the first postdosing metHb was taken after 2 hours. Hence, this derivation will be applied only to those patients who had first postdosing metHb before 2 hours.

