5.1.3. Summary of metHb

The treatment effect on metHb will be evaluated based on change in metHb from baseline. Because of the wide range in assessment times, the summary table will include only 2 time points: Baseline (last metHb before treatment) and predicted metHb at 1-hour posttreatment. The table will provide descriptive statistics for the observed metHb level, change from baseline, and percent change from baseline, including sample size, mean, standard deviation, and 2-sided 95% confidence intervals for the mean, minimum, median, and maximum. Number (%) patients with $\geq 50\%$ metHb reduction 1 hour posttreatment will be identified. (Table 14.2.1.1). This table will also include predicted time when metHb 50% reduction would occur and time when the first metHb is obtained.

[figure not shown]
A second summary table (Table 14.2.1.2) will provide metHb level descriptive summary at baseline and metHb level of the first follow-up posttreatment for all patients in the efficacy analysis set. In this table, the level of metHb at the first follow-up and time when the first follow-up metHb is taken will be summarized.

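### The T50 derivation has no rule for patients whose metHb did not fall: a rise gives a negative time and no change gives no value

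*SAP*

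**What the plan says.** SAP 5.1.2 introduces T50 with "To estimate the time when a 50% reduction would be obtained, the following linear interpolation will be applied". The formula uses two measurements only: the last metHb before the first infusion and the first one after it. The section gives one condition on who receives a T50: "this derivation will be applied only to those patients who had first postdosing metHb before 2 hours".

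The population is the efficacy analysis set, defined in SAP 3.2 as "all safety analysis set patients who have at least 1 metHb assessment before and after ProvayBlue™ infusion and who are Primary cases". A fall in metHb is not required. SAP 3.5, on missing data, covers only a missing infusion stop time and says nothing about a T50 that is negative or cannot be computed.

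The result goes into Table 14.2.1.1. SAP 5.1.3 says: "This table will also include predicted time when metHb 50% reduction would occur and time when the first metHb is obtained". It names no statistic for T50. SAP 4 lists sample size, mean, standard deviation, minimum, median and maximum as the usual summary of a continuous variable where appropriate, given for all patients and separately for dapsone and non-dapsone patients.

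**The concern.** The denominator of T50 is the drop from baseline to the first sample, divided by time. It therefore carries the sign of that drop. A patient whose metHb rose has no time of 50% reduction, yet the formula returns one, and it is earlier than that of any responder. A patient whose metHb did not move gets a division by zero.

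Patients with no early fall are foreseeable. SAP 3.7.2 sets dapsone cases apart because of the drug's long half-life, "which likely results in ongoing production of metHb through the acute treatment phase". The package insert appended to the protocol (5.3) warns that methemoglobinemia due to dapsone may not resolve.

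With no rule in the plan, the handling is left to whoever programs the table, with the data in hand. The two obvious choices, keeping the negative value or setting it to missing, both make T50 look better than it should. The cells are small: SAP 1 gives 7 and 24 enrolled patients, 31 in all, before restriction to Primary cases sampled inside 2 hours and before the split by causative agent.

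**Working it through.** **Inputs from the SAP.** In the 5.1.1 example, "a patient has metHb of 74.40 at baseline and 15.70 at 70 minutes postdosing". In 5.1.2, "T50 for the above example is 44 minutes".

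**Reproducing the SAP's figure.** Write b for baseline, m for the first post-dose metHb and t for its time in minutes:

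T50 = (b/2) / [(b - m)/t]

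T50 = 37.2 / [(74.4 - 15.7)/70] = 37.2 / 0.83857 = 44.36 minutes, as stated.

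This needs the factor 60 in the printed formula to be left out. With it the result is 0.74, which is in hours although labelled minutes. The printed example line also has 74 for 74.4 and a stray division by 74.4. These are separate slips; a positive constant in the denominator changes neither the sign of T50 nor the division by zero.

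**Behaviour by type of outcome.** Assumed inputs, not in the documents: b = 40, t = 60. Then T50 = 20 / [(40 - m)/60] = 1,200/(40 - m) minutes.

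| First value m | Change | T50 |
|---|---|---|
| 15 | large fall | 48 min |
| 20 | fall of exactly 50% | 60 min |
| 30 | partial fall | 120 min |
| 38 | small fall | 600 min (10 h) |
| 39 | very small fall | 1,200 min (20 h) |
| 40 | none | undefined |
| 41 | rise | -1,200 min (-20 h) |
| 42 | rise | -600 min (-10 h) |
| 44 | rise | -300 min (-5 h) |
| 50 | rise | -120 min (-2 h) |

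Three points follow.

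- T50 exceeds t exactly when b - m is less than b/2. Below a 50% fall the result is therefore an extrapolation beyond the sample, although the SAP calls it interpolation. The order is still right: a smaller fall gives a longer time.
- An unchanged value gives no number, so the patient would be missing from the summary.
- Any rise gives a negative time. Among risers the order is also perverse, since the smallest rise gives the most negative value.

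**Effect on a summary.** Assumed data: eight responders with T50 of 0.60, 0.65, 0.70, 0.75, 0.80, 0.85, 0.90 and 0.95 h. Their sum is 6.20 h and their mean and median are both 0.775 h.

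- One riser kept at -5 h: mean (6.20 - 5)/9 = 0.13 h; median (5th of 9) 0.75 h; minimum -5 h.
- The same riser ranked last as not reached: median (5th of 9) 0.80 h.
- Two risers kept at -5 h and -10 h: mean (6.20 - 15)/10 = -0.88 h; median (0.70 + 0.75)/2 = 0.725 h.
- The same two ranked last: median (0.80 + 0.85)/2 = 0.825 h.
- One or two patients with no fall dropped as missing: mean and median stay at 0.775 h on 8 patients, with no trace of the failures.

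The median thus moves by 0.05 h (3 minutes) with one riser and by 0.10 h (6 minutes) with two. The mean becomes uninterpretable.

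**The case against.** A reader might infer that treatment failures in general are averaged in as the fastest responders. The documents do not support that. Only a net rise gives a negative time. An unchanged patient has no value to average. A failure with a small fall gets a long positive T50 and sorts as slow, which works against the drug. Averaging is itself an inference: SAP 5.1.3 names no statistic for T50, the general list in SAP 4 applies only where appropriate, and nowhere does the SAP say that negative times are kept.

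The case may also never arise. No document reports a patient whose first sample was at or above baseline. In the historical series in protocol 6.5, 15/17, 12/13 and 16/17 patients had at least a 50% fall within 1 hour. That is 43 of 47, so at most 4 could have had no fall. Continuing metHb production under dapsone implies a slower net decline, not necessarily a rise, and a later rebound would not enter T50.

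Nor would the error be well hidden. A negative minimum is conspicuous, Listing 16.2.8 shows derived metHb parameters by patient, and each patient's metHb course is plotted. The primary endpoint in SAP 3.3.1, the proportion with at least a 50% reduction at the first available assessment, does not use T50, and no inferential testing is planned.

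All of this stands, and it limits the severity. It does not supply the missing rule. Visibility helps with a negative value but less with an unchanged patient, who simply leaves the denominator. Rarity is little comfort in groups this small, where one patient can set the minimum and swing a mean.

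**Conclusion.** The point holds in limited form. Applied as written, SAP 5.1.2 returns an impossible negative time for a patient whose metHb rose and no value for one whose metHb was unchanged, and no other section corrects this. If negative values are kept, such a patient ranks fastest and becomes the minimum of Table 14.2.1.1; if they are set to missing, a failure disappears.

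On the assumed data above, the median shifts by 3 to 6 minutes, while the mean falls from 0.775 h to 0.13 h or -0.88 h. These sizes rest on invented values, on negatives being kept and, for the mean, on a mean being reported. The sign and the division by zero rest on none of these.

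T50 is a descriptive, supportive quantity. The primary endpoint is unaffected, and so is the count of patients with at least a 50% reduction at 1 hour in the same table. Severity is minor to moderate.

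**What to change.** In SAP 5.1.2, state that T50 is not derived when the first post-dose metHb is at or above baseline, and that these patients are recorded as not reached.

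In SAP 5.1.3, for Table 14.2.1.1 overall and in each causative-agent group:

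- report the number with a derived T50 out of N, and the number not reached;
- summarise T50 by a median that ranks not-reached patients last, in place of a mean;
- flag any T50 later than the first sample as extrapolated.

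Extrapolated times for partial responders can stay, since they are correctly ordered. Barring them, censoring at the first sample or using Kaplan-Meier methods is not needed to cure this defect, and censoring there would ignore later samples that show the fall.

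The cost is a few sentences and a few lines of code, with no new data. The reported median may come out slightly slower.

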5.1.3. Summary of metHb

The treatment effect on metHb will be evaluated based on change in metHb from baseline. Because of the wide range in assessment times, the summary table will include only 2 time points: Baseline (last metHb before treatment) and predicted metHb at 1-hour posttreatment. The table will provide descriptive statistics for the observed metHb level, change from baseline, and percent change from baseline, including sample size, mean, standard deviation, and 2-sided 95% confidence intervals for the mean, minimum, median, and maximum. Number (%) patients with $\geq 50\%$ metHb reduction 1 hour posttreatment will be identified. (Table 14.2.1.1). This table will also include predicted time when metHb 50% reduction would occur and time when the first metHb is obtained.

[figure not shown]
A second summary table (Table 14.2.1.2) will provide metHb level descriptive summary at baseline and metHb level of the first follow-up posttreatment for all patients in the efficacy analysis set. In this table, the level of metHb at the first follow-up and time when the first follow-up metHb is taken will be summarized.

5.1.4. Individual Profile of metHb

Individual profiles of metHb over time will be prepared for each patient. All metHb assessments will be included. The profile will flag if the patient is a Primary case or a Secondary case.

The change from baseline in metHb will also be graphically presented, showing the change from baseline by time (hours) for each patient (Figure 14.2.1.3) as illustrated in Figure 1.

Figure 1: Example of Individual Profile of metHb Before and After Treatment

Hour 0 is when the first dose of ProvayBlueTM infusion is completed and the dotted vertical reference line is 1 hour after the end of infusion.

5.2. Change in Vital Signs

Vital signs change from baseline, including blood pressure, respiratory rate, and heart rate, will be derived for each patient. Baseline is the last vital sign measurement before a patient receives the first infusion of ProvayBlueTM.

5.2.1. Median Vital Signs within 2-Hour Post Treatment

Vital signs measurements, including systolic blood pressure, diastolic blood pressure, heart rate and respiratory rate, were taken at various time points and frequency. In order to synchronize the measurements, all vital signs measures taken within 2 hours will be pooled within each individual patient dataset to derive the median for the patient.

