7.2.2. Secondary Efficacy Endpoints

- Concomitant normalization of the respiratory rate, heart rate and blood pressure (see standard values in Section 13.1) within 2 hours of the first dose of ProvayBlueTM;
- Evaluation of the patients who achieve a 50% reduction in metHb level after a single dose of ProvayBlueTM, in addition to normalization of the respiratory rate, heart rate and blood pressure;
- Evaluation of the number of patients who achieve a 50% reduction in metHb level within one hour after treatment with ProvayBlueTM in addition to normalization of the respiratory rate, heart rate and blood pressure within 2 hours of receiving the first dose of ProvayBlueTM;

• Evaluation of the patients who achieve a 50% reduction in metHb level after a second dose of ProvayBlueTM, in addition to normalization of the respiratory rate, heart rate and blood pressure, in cases where a single dose did not completely normalize metHb level;

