8. INVESTIGATIONAL PLAN

8.1. SUMMARY OF STUDY DESIGN

This is an open label, uncontrolled Phase 4 study of 10 patients who present in hospital/urgent care setting with acquired methemoglobinemia. The population may include pediatric and adult patients (males and females of all ages are included).

The aim of the study is to confirm safety and efficacy of ProvayBlueTM for the treatment of acquired methemoglobinemia.

This study comprises of an analysis of data for patients presenting with acquired methemoglobinemia and requiring ProvayBlueTM. The analysis itself will focus on clinical outcome of treatment with ProvayBlueTM alone. If possible, depending on the number of patients, the data will be summarized by age, sex and body weight.

The study will include sites which will be based in France, Germany, UK and the US.

ProvayBlueTM will be administered IV at a dose of 1 mg/kg over 5-30 minutes. If the metHb level remains greater than 30% or if clinical signs and symptoms persist, a repeat dose of 1 mg/kg may be given 1 hour after the first dose.

Depending on the clinical status of the patient, additional doses may be administered at the discretion of the Investigator. The data on these additional doses will be recorded in the study Case Report Form (CRF).

[figure not shown]
Due to the nature of the disease and indication, the patient's treatment with ProvayBlueTM may take place per the Investigator's standard of care prior to or after Patient Informed Consent Document (PICD) signature. Data collection (retrospective and prospective) for this study and study specific assessments will only take place after PICD signature.

Safety will be monitored throughout the study by repeated clinical and laboratory evaluations according to protocol requirements.

The expected duration of the study will vary for each patient depending on the clinical situation and outcome of treatment. Patients will be followed-up 5 to 10 days (follow-up visit), and 10 to 15 days (follow-up call) after the last administration of ProvayBlueTM. End of study is defined as the Last Patient Last Visit (LPLV).

The study design is summarized in Figure 8-1.

Figure 8-1: Study Design

A schedule for the tests and evaluations to be conducted in this study is found in the flow chart in APPENDIX 2:Study Flow Chart.

The study duration of the trial will vary for each patient depending on the clinical situation and outcome of treatment.

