8.3. TRIAL TIMETABLE (STUDY PERIODS)

The trial includes the following visits:

- Screening and enrolment
- Study Treatment
 - H0: ProvayBlueTM Dose 1
 - H1: 1 hour after the end of ProvayBlueTM infusion. Administration of ProvayBlueTM Dose 2 (if applicable)
 - H2: 2 hours after the end of ProvayBlue™ Dose 1 infusion
 - H3: 2 hours after the end of ProvayBlueTM Dose 2 infusion (if applicable)
- H24 (24 hours after the end of ProvayBlueTM Dose 1 infusion)
- Hospital Discharge (if earlier than H24)
- Follow up visit (5 -10 days following the last ProvayBlueTM administration)
- Follow up call (10 -15 days following the last ProvayBlueTM administration)

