12.2. TREATMENT

Due to the nature of the disease indication, the patient's treatment with ProvayBlueTM as per standard of care can take place prior to or after PICD signature. Data collection (retrospective and prospective) for this study and study specific assessments will only take place after PICD signature.

Refer to APPENDIX 2: Study Flow Chart for data collection time points and schedule of assessments.

Assessments during treatment and the relevant collection of data (as per standard of care) include the following:

- ProvayBlueTM administration (including dose, lot number, date, time and route of administration, and if any dilution took place);
- Clinical symptoms related to methemoglobinemia and severity:
 - Within 1 hour after the end of each ProvayBlueTM infusion (i.e. both Dose 1, Dose 2 and any additional dose if applicable);

- Within 2 hours after the end of each ProvayBlue[™] infusion (i.e. both Dose 1, Dose 2 and any additional dose if applicable);
- Approximately 24 hours post the end of the last ProvayBlueTM infusion, or just prior to discharge from the clinic if earlier than 24 hours.
- Vital signs (refer to Section 15.2.2 for the list of parameters):
 - o Within 1 hour after the end of each ProvayBlue[™] infusion (i.e. both Dose 1, Dose 2 and any additional dose if applicable);
 - o Within 2 hours after the end of each ProvayBlue™ infusion (i.e. both Dose 1, Dose 2 and any additional dose if applicable);
 - o Approximately 24 hours post the end of the last ProvayBlue™ infusion, or just prior to discharge from the clinic if earlier than 24 hours.
- Blood sample for:
 - o Biochemistry, hematology and metHb (refer to Section 15.2):
 - Within 1 hour after the end of each ProvayBlueTM Dose 1 infusion (i.e. Dose 1, Dose 2 and any additional dose if applicable);
 - Prior to ProvayBlueTM Dose 2 if applicable (i.e., if the metHb level is acceptable within 1 hour after the end of Dose 1 ProvayBlueTM infusion, the repeat dose of ProvayBlueTM will not be needed);
 - Approximately 24 hours post the end of the last ProvayBlueTM infusion, or just prior to discharge from the clinic if earlier than 24 hours.
 - o PK analysis (refer to Section 14):
 - Approximately 1 hour after the end of each ProvayBlueTM infusion (i.e. Dose 1, Dose 2 and any additional dose if applicable);
 - Prior to Dose 2 (or any additional dose) ProvayBlueTM infusion (if applicable);

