5.2.2. Vital Signs Normal/Abnormal Assessments

Change from baseline in **vital signs (blood pressure, respiratory rate, and heart rate)** after the first dose of ProvayBlue™ infusion will be evaluated.

- The secondary efficacy will be the number (%) of patients with concomitant normalization of vital signs (as per the clinical context) within 2 hours, inclusive, after the end of infusion of the first dose of ProvayBlue™
- Time (hours) when the first incidence of normal VS is observed in patients who have abnormal baseline vital signs

The normal ranges used to define normal blood pressure are provided in Table 4. However, in the individual patient narratives, vital signs will be contextualized for comorbidity and other pertinent issues. For example, a patient with chronic obstructive pulmonary disease likely has an elevated respiratory rate even when not suffering for acquired methemoglobinemia; a “return to normal” for such a patient would be clinically expected to differ from “return to normal” for a patient without COPD.

Table 4: Vital Signs Normal Ranges

Population	Systolic Blood Pressure (SBP) mmHg	Diastolic Blood Pressure (DBP) mmHg	Respiratory Rate (RC) Breaths/min	Heart Rate (HR) Beats/min
Birth (12 hours)	60-76	31-45	30-60	120-140
Neonate (96 hours)	67-84	35-53		
Infant (1 to 12 months)	72-104	37-56		
Children (1 to 2 years)	86-106	42-63	22-40	80-110
Children (3 to 5 years)	89-112	46-72	20-28	60-70
Children (6 to 9 years)	97-115	57-76	18-25	70-80
Children (10 to 11 years)	102-120	61-80		
Adolescent (12 to 15)	110-131	64-83	12-20	60-70
Adults (\geq 16 years)	90-140	60-90	12-20	50-100

All assessments (with and without assessment time) will be included in the data listing (Listing 16.2.9).

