5.2.3. Summaries of Vital Signs Change from Baseline

A summary table will include VS measurement and change from baseline by relative time frame with descriptive statistics of sample size, mean, standard deviation, 2-sided 95% confidence intervals, quartiles (25% tile, 50% tile [median], and 75% tile), minimum, and maximum. The table will also include number (%) patients whose vital signs are within the normal range (Table 14.2.2.1). Number (%) patients who had at least 1 incidence of normal vital signs within the 2 hours following the completion of first dose ProvayBlueTM infusion will also be presented.

Change in SpO₂ will be assessed in 3 categories, based on $\pm 2\%$ rule as follows

- 1) Increased if the difference (postbaseline – baseline) is >2
- 2) No Change if the difference (postbaseline – baseline) is within ± 2
- 3) Decreased if the difference (postbaseline – baseline) is <2

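### The 2-hour vital-sign results after the first infusion have no rule for readings taken after a second dose, so normalization that follows Dose 2 can be reported as a first-dose effect

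*SAP*

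**What the plan says.** **Endpoint and rules in the SAP.** The vital-sign endpoint (SAP 3.3.1 and 5.2.2) is the number of patients normalized "within 2 hours, inclusive, after the end of infusion of the first dose of ProvayBlue™". Because readings come at irregular times, SAP 5.2.1 sets the rule that "all vital signs measures taken within 2 hours will be pooled within each individual patient dataset to derive the median for the patient". SAP 5.2.3 adds to Table 14.2.2.1 a count of patients with "at least 1 incidence of normal vital signs within the 2 hours following the completion of first dose" of the drug. None of SAP 5.2.1 to 5.2.3 mentions Dose 2.

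**Timing of Dose 2 in the protocol.** The timetable in Protocol 8.3 reads "H1: 1 hour after the end of ProvayBlueTM infusion. Administration of ProvayBlueTM Dose 2 (if applicable". Protocol 8.1 says that "a repeat dose of 1 mg/kg may be given 1 hour after the first dose", on condition that metHb stays above 30% or signs and symptoms persist. Each infusion lasts 5 to 30 minutes.

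**Timing of readings.** Protocol 12.2 and the flow chart ask for vital signs within 1 hour and within 2 hours after the end of each infusion. For metHb, hematology and biochemistry, Protocol 12.2 adds a draw "Prior to ProvayBlueTM Dose 2 if applicable"; vital signs have no such time point. In the Observational Study, which the SAP pools with this trial, timing follows institutional care (SAP 2.1).

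**What the protocol wants to learn.** Protocol 7.1.2 has separate objectives for a single dose and for a second dose. Protocol 7.2.2 has one endpoint on "Evaluation of the patients who achieve a 50% reduction in metHb level after a single dose of ProvayBlueTM, in addition to normalization" of vital signs, and another for the second dose. Protocol 13.2 assesses secondary endpoints for 2 hours after each dose.

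**The concern.** If Dose 2 starts about an hour after Dose 1, the 2-hour window for Dose 1 and the 2-hour window for Dose 2 overlap, and no rule assigns the overlap. SAP section 5 plans no second-dose vital-sign summary, so any benefit of Dose 2 that appears inside the first window can only show up in the result attached to the first dose.

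This matters because Protocol 6.1 and 8.2 name normalization of respiratory rate, heart rate and blood pressure within 2 hours of the first dose among the minimal efficacy endpoints of the post-marketing requirement. A reader of Table 14.2.2.1 would not know how many of the normalized patients needed a second dose first.

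**Working it through.** The documents state no figure on this point, so there is none to reproduce. Take time 0 as the end of the first infusion; the window is 120 minutes.

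**1. Share of the window after Dose 2 starts.** Share = (120 − start of Dose 2) / 120.
- Hour counted from the end of Dose 1, as H1 is defined in Protocol 8.3: start = 60, share = 60/120 = 50%.
- Hour counted from the start of Dose 1, a possible reading of Protocol 8.1: start = 60 − duration of Dose 1. For 5 minutes, start = 55 and share = 65/120 = 54%. For 30 minutes, start = 30 and share = 90/120 = 75%.

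**2. Scheduled readings in the window, Dose 2 at H1.** One reading is due by 60 minutes and one by 120 minutes. Dose 2 ends at 65 to 90 minutes, so the latest time for its own 1-hour reading is 125 to 150 minutes, outside the window. If that reading is taken early, 2 of 3 readings follow Dose 2. On the second reading of the hour, the within-1-hour set after Dose 1 could itself fall after Dose 2 has started.

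**3. What the two rules do.** Illustrative adult respiratory rates; the normal range in SAP Table 4 is 12 to 20.

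| Before Dose 2 | After Dose 2 | Median | Median rule | At least one normal | Before Dose 2 only |
|---|---|---|---|---|---|
| 24 | 16 | 20 | normal | yes | not normal |
| 28 | 18, 16 | 18 | normal | yes | not normal |
| 28 | 16 | 22 | not normal | yes | not normal |
| 18 | 24 | 21 | not normal | yes | normal |

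Extra readings can add a success to the at-least-one count but never remove one. The median can move in either direction, as the last row shows.

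**4. Size per patient.** One misclassified patient moves the rate by 100/N points. Enrollment was 7 and 24 (SAP section 1), so pooled N is at most 31: 100/31 = 3.2 points. Secondary cases are excluded from the efficacy set, so N will be smaller if there are any, and the step larger. With all 7 Interventional Study patients, 100/7 = 14.3 points.

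**5. Total size, under assumptions only.** Overstatement = (share given Dose 2 within the window) × (share of those normal only afterwards). The documents give neither factor. Assuming 10% to 40% for the first and 25% to 90% for the second, the range is 0.10 × 0.25 = 2.5 points to 0.40 × 0.90 = 36 points. A range this wide shows only that the size cannot be judged from the documents.

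**The case against.** The best defence is that the endpoint the SAP carries forward is anchored in time to the first dose and is not conditional on receiving no second dose. It follows the wording of the post-marketing requirement. Counting normalization regardless of re-dosing is a legitimate choice, and the 2-hour result should stay. What the defence does not supply is a statement that this was the choice. Nor does a result regardless of re-dosing answer the protocol's single-dose objective.

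A second defence is that results are descriptive (SAP 3.4), doses received are tabulated (SAP 6.1), individual profiles are plotted (SAP 5.2.4), and dosing and vital signs are listed (Listings 16.2.5 and 16.2.9). A careful reader could reconstruct single cases where times are recorded. That helps, but it does not change or label the rate in Table 14.2.2.1.

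Three stronger readings are tempting and are not supported:
- *That no vital signs are scheduled before Dose 2.* In the Interventional Study a set is due within 1 hour after the end of Dose 1, hence by H1. What is missing is a time point tied to Dose 2, as the blood samples have.
- *That the window lies mostly after Dose 2.* With Dose 2 at H1 the split is exactly half.
- *That re-dosed patients are all first-dose failures, so that the affected share equals the re-dosing rate.* Re-dosing depends on metHb or symptoms, not on vital signs. From the SAP's own example baseline of 74.4, a fall to 35 is a reduction of 39.4/74.4 = 53%. That patient meets the 50% criterion, may still be re-dosed because 35 exceeds 30, and may already have normal vital signs.

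**Conclusion.** The point holds in a limited form. SAP 5.2.1 to 5.2.3 leave readings after Dose 2 unaddressed. A patient who was abnormal before Dose 2 and normal only after it can be reported as normalized after the first dose, under either rule. The bias is one-directional for the at-least-one-normal count and of uncertain direction for the median.

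Only patients who are re-dosed inside the window, are abnormal beforehand and are normal afterwards can be wrongly credited to the first dose. Their number is unknown. Each moves the pooled rate by at least 3.2 points, or by 14.3 points among the 7 Interventional Study patients. The 50% share of the window rests on the H1 definition; the 54% to 75% range rests on counting the hour from the start of Dose 1. Protocol 8.1 and 8.3 must be reconciled on this. The documents do not support a claim that the 2-hour endpoint is itself wrong or that the result is inflated by a known amount.

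**What to change.** In SAP 5.2.1 to 5.2.3 and Table 14.2.2.1:
1. Keep the 2-hour result and label it as regardless of Dose 2.
2. Add a line, for both the median and the at-least-one-normal count, that uses only readings from the end of the first infusion to 2 hours or the start of the second infusion, whichever is earlier. Give the number of patients with no reading in that interval.
3. Show the results by whether Dose 2 was given within the window.
4. State that the cut shortens follow-up for re-dosed patients, some of whom might have normalized by 2 hours on the first dose alone. The added line is therefore a conservative single-dose estimate and does not replace the 2-hour result.

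A change to the visit schedule would serve no purpose, because enrollment closed on 31 August 2020.

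The cost is one derivation rule and a few table rows, using the infusion and vital-sign records already planned for the pooled database (SAP Table 3). It assumes that start times of second infusions were recorded; patients without one should be shown as undetermined. The downside is a possibly less favourable rate and fewer readings per re-dosed patient.
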